6.5.1. Adverse Events

Adverse events will be reported in accordance with the CaPS.

Participant discontinuations due to adverse events will be detailed. Data will be reported in accordance with the CaPS.

6.5.2. Laboratory Data

Laboratory data will be listed and summarized in accordance with the CaPS.

6.5.3. Vital Signs

Vital sign data will be databased and available upon request.

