9.3.1. Safety Analyses

Vital signs, AEs and safety laboratory data will be reviewed and summarized on an ongoing basis during the study to evaluate the safety of participants. Safety data will be presented in tabular and/or graphical format and summarized descriptively, where appropriate.

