2.1. Modifications to the Analysis Plan Described in the Protocol

None.

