3.5. Safety Endpoints

The following data are considered in standard safety summaries (see protocol for collection days, baseline assessment, and list of parameters):

- Adverse Events (AE)
 - o Treatment-emergent AEs
 - Treatment related AEs
 - SAEs and AEs leading to discontinuation
- Clinically significant abnormalities in vital signs
- Clinically significant abnormalities in clinical laboratory values.

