3.5.2. Vital Signs

Blood Pressure (BP) and Pulse Rate (PR) will be measured at times specified in the SoA given in the protocol. The baseline measurement is the latest measurement during the Screening period.

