3.5.3. Laboratory Data

Safety laboratory tests will be performed as described in the protocol. To determine if there are any clinically significant laboratory abnormalities, the haematological, clinical chemistry (serum) and urinallysis safety tests will be assessed against the criteria specified in the

sponsor reporting standards. The assessment will not take into account whether each participants' baseline test result is within or outside the laboratory reference range for the particular laboratory parameter.

For each laboratory parameter, the baseline measurement is the latest measurement during the Screening period.

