5.3.3. Safety Data

Missing values in standard summaries of AEs, laboratory data, and vital signs will be imputed according to CaPS.

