6.5. Safety Summaries and Analyses

All safety analyses will be performed on the Safety Analysis Set.

Safety data will be presented in tabular and/or graphical format and summarized descriptively, where appropriate.

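### Clinically significant vital-sign abnormalities are a declared secondary endpoint, but SAP 6.5.3 plans no output for vital signs

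*SAP*

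**What the plan says.** The endpoint "Clinically significant abnormalities in vital signs" appears in SAP 3.5 and in the SAP 2.2 objectives table. The protocol synopsis and the protocol's objectives table list it as well. SAP 3.2.3 confirms that safety data count as secondary endpoints, and SAP 6.2.4 refers the reader to Section 6.5 for their analysis.

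Within Section 6.5, adverse events are reported under the sponsor's data standards (6.5.1) and laboratory data are listed and summarized under the same standards (6.5.2). For vital signs, 6.5.3 consists of one sentence: "Vital sign data will be databased and available upon request".

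Other parts of the plan read as though a vital-sign summary will exist:

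- Protocol 9.3.1: "Vital signs, AEs and safety laboratory data will be reviewed and summarized on an ongoing basis during the study to evaluate the safety of participants".
- SAP 3.5.2, for vital signs: "The baseline measurement is the latest measurement during the Screening period".
- SAP 5.3.3: "Missing values in standard summaries of AEs, laboratory data, and vital signs will be imputed according to CaPS".
- SAP 6.5: "Safety data will be presented in tabular and/or graphical format and summarized descriptively, where appropriate".

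SAP 2.1, headed "Modifications to the Analysis Plan Described in the Protocol", states that there are none.

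**The concern.** A declared endpoint needs a planned output. Here the section that should supply it says only that the data will be held and provided if someone asks. A programmer who follows 6.5.3 can defensibly produce nothing, while one who follows 3.5 and 5.3.3 would expect to build a standard summary. The SAP does not say which governs.

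The SAP also leaves open what makes a vital-sign value clinically significant. For laboratory results, SAP 3.5.3 says the "safety tests will be assessed against the criteria specified in the" sponsor's reporting standards. SAP 3.5.2 has no counterpart for blood pressure or heart rate.

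At stake is the completeness of safety reporting in a study of children aged 6 to under 12. The study report could give no count for one of its named safety endpoints, and a reader could not see the values behind any vital-sign event.

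**Working it through.** The plan gives no figure on this point, so the check is a comparison of sections followed by a count of the data involved.

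**Step 1: is it an endpoint?** Yes. It is in the objectives tables of both documents and in SAP 3.5, and SAP 3.2.3 gives safety data secondary-endpoint status.

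**Step 2: which section delivers it?** SAP 6.2.4 sends safety data to Section 6.5, where the treatment differs by data type:

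| Data | SAP section | Planned output |
|---|---|---|
| Adverse events | 6.5.1 | Reported under sponsor standards |
| Laboratory data | 6.5.2 | Listed and summarized |
| Vital signs | 6.5.3 | Stored only |

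The other declared endpoints are all summarized: AUC24 (6.1), the remaining PK parameters (6.2.1), PD (6.2.2) and taste (6.2.3). Exposure and concomitant medication, which are not endpoints, are listed (6.4.3, 6.4.4).

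**Step 3: does another section supply the output?** No. SAP 3.5 and 5.3.3 assume standard summaries but specify none. The sentence in SAP 6.5 is general, is qualified as applying where appropriate, and does not name vital signs. The specific section, 6.5.3, says otherwise. The vital-signs baseline defined in 3.5.2 is used by no specified output.

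**Step 4: how much of the safety endpoint set is affected?** SAP 2.2 lists five groups: treatment-emergent AEs; treatment-related AEs; SAEs and AEs leading to discontinuation; vital-sign abnormalities; laboratory abnormalities. One of the five has no output of its own.

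**Step 5: how much data is involved?** The Schedule of Activities places vital signs at Screening and Day 7. Protocol 8.3.2.1 records the average of three blood pressure readings and a single heart rate. Assuming systolic and diastolic pressure are recorded separately:

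- Per child: (1 systolic + 1 diastolic + 1 heart rate) × 2 visits = 6 values.
- 12 children: 6 × 12 = 72 values, of which 3 × 12 = 36 are from Day 7.
- 15 children, if all three replacements allowed in the synopsis are used: 6 × 15 = 90 values, of which 3 × 15 = 45 are from Day 7.

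These counts show how small the reporting task is. They do not measure bias. Fifteen is not a firm ceiling, because protocol 4.1 asks for at least 12 evaluable participants and repeats no cap on replacements.

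**The case against.** The strongest reply is that 6.5.3 concerns the raw measurements, whereas the endpoint is clinically significant abnormalities, which SAP 3.5 places among the standard safety summaries. On that reading nothing is missing. It fails because no section specifies such a summary, and because the parallel section 6.5.2 is where the laboratory endpoint is delivered.

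A second reply is that the information is reported anyway. Protocol 10.3.1 makes a vital-sign result an AE when the investigator considers it clinically significant, protocol 8.3.2 requires findings that meet the AE definition to be reported, and SAP 6.5.1 reports AEs. This stands in part: what is missing is a separate display, not every trace of the event. It also supplies a candidate definition of clinical significance, investigator judgment, although the SAP does not adopt it. But clinically significant laboratory findings take the same AE route and still receive their own listing and summary, and both documents list vital-sign abnormalities separately from the AE endpoints.

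A third reply is that protocol 9.3.1 mainly describes monitoring during the study, and that its sentence on presentation applies only where appropriate. This is fair. It weakens the charge that SAP 2.1 is wrong to declare no modification. The conflict within the SAP does not depend on it.

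Finally, the harm is limited: the study is open-label with seven days of dosing, about 12 children and no hypothesis test, and the values could be requested. That bears on priority. It does not close the gap.

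**Conclusion.** The concern holds. SAP 6.5.3 as written leaves a declared secondary safety endpoint, one of five listed groups, without a table, listing or count of its own, and it conflicts with SAP 3.5 and 5.3.3. The SAP also does not state how a clinically significant vital-sign abnormality is identified.

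The conclusion assumes that the specific section prevails over the general sentence in 6.5. If the sponsor intends the reverse, 6.5.3 still has to be rewritten. No protocol amendment was needed merely to change the reporting of a secondary endpoint, since both documents allow the SAP to modify the plan. The procedural fault is that any such change was not declared in SAP 2.1, and that part is less certain than the rest.

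The practical effect is modest and confined to descriptive safety reporting. This should be corrected, but it does not threaten the study's main result.

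**What to change.** Before database release, replace SAP 6.5.3 with text along these lines: *Blood pressure and heart rate at Screening and Day 7 will be listed and summarized descriptively for the Safety Analysis Set. The number and percentage of participants with a clinically significant vital-sign abnormality will be presented.*

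State in SAP 3.5.2 how clinical significance is determined: either investigator judgment, as in protocol 10.3.1, or the sponsor's reporting standards, as SAP 3.5.3 does for laboratory data. The endpoint strictly needs only the count and a listing of flagged abnormalities. With so few values, listing and summarizing all of them adds little work and uses the baseline already defined.

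If the sponsor does not want this output, it should declare the departure in SAP 2.1, amend the endpoint in the protocol and in SAP 2.2 and 3.5, and bring 5.3.3 into line.

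The first route costs one SAP paragraph, one listing and one short table from data already on the CRF. It needs no new data collection and no change to the primary analysis.

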7. INTERIM ANALYSES

No formal interim analysis will be conducted for this study. As this is an open-label study, the sponsor may conduct unblinded reviews of the data during the course of the study for the purpose of safety assessment, facilitating PK modeling, and/or supporting clinical development.

Final analysis will follow the official database release. As this will be an open-label study, there is no formal unblinding of the randomization code.

APPENDICES

Appendix 1. List of Abbreviations

Abbreviation	Term
AA	alopecia areata
ADL	activity/activities of daily living
AE	adverse event
AESI	adverse event of special interest
AUC	Area under the concentration-time curve
AUC ₂₄	Area under the plasma concentration time profile over the dosing
	interval 24 hrs, at steady-state
BLQ	below the limit of quantitation
BP	blood pressure
CaPS	CDISC and Pfizer Standards
CDISC	Clinical Data Interchange Standards Consortium
C-SSRS	Columbia – Suicide Severity Rating Scale
CL	apparent clearance
CL/F	apparent clearance after oral dose
C_{max}	maximum plasma concentration
CTCAE	Common Terminology Criteria for Adverse Events
eSAE	electronic serious adverse event
HR	heart rate
IQR	Interquartile Range
NK	natural killer
OIRC	Opportunistic Infection Review Committee
PD	pharmacodynamic(s)
PK	pharmacokinetic(s)
QD	once daily
SAE	serious adverse event
SALT	Severity of Alopecia Tool
SAP	Statistical Analysis Plan
SC	subcutaneous(ly)
SoA	schedule of activities
TEAE	Treatment emergent adverse event
T_{max}	time to reach C _{max}
t½	terminal elimination half-life
V _Z /F	Apparent volume of distribution after oral dose
WOCBP	woman/women of childbearing potential
